Bionutrition Visit (prior to both Baseline Visit 1 and 12 Month Visit): Subjects will be tested on an ad lib diet, after an overnight 12 hr fast. We will obtain:

- 1) Blood for Cr, K, lipids, glucose, insulin, CD4/8, HIV viral load (12 Month Visit only) and biomarkers for vascular dysfunction (sICAM, sVCAM), inflammation/ immune activation (CRP, IL6, MCP-1, sCD14, sCD163), subclinical injury (BNP, high

**Mineralocorticoid Receptor Antagonism for Cardiovascular Health in HIV
The MIRACLE HIV Study**

sensitivity cardiac troponin T [hs-cTnT]), and fibrosis (galectin-3, cardiotrophin 1[CT1], lipocalin 2, PINP, PIINP). DNA collection for genetic testing is optional.

- 2) 24 hr urine collection for sodium (Na) and Cr for sodium balance will be started one day prior to the visit. In consultation with the bionutritionist, broth packets will be given to achieve standardized sodium conditions (urinary Na >200mmol/24 hr) for Baseline Visit 1 and 12 Month Visit. Urine pregnancy test for females as appropriate.
- 3) Standardized lifestyle counseling as per goals derived from the AACE and NCEP-ATP III guidelines and modeled after the Diabetes Prevention Program.
- 4) Coronary CTA only at the end of study visit prior to 12 Months. (This will not be performed if the subject has a previous reaction or contraindication to iodine-containing contrast media).
- 5) Optional Consent for substudy.

Baseline Visit 1 (Imaging): Subjects will present after a 12 hr fast on 2 consecutive days. CCB will be held 36 hrs prior to coronary perfusion assessment.

- 1) 24 hr urine will begin on the morning of this visit for volume, Na, K, Cr, cortisol and aldosterone excretion rate.
- 2) STAT serum pregnancy test for females as appropriate.
- 3) Urine Na and Cr for sodium balance.
- 4) Interval history and physical, including orthostatics.
- 5) Cardiac PET to assess CFR.
- 6) Subjects will begin fast and lie supine overnight.
- 7) Fasting blood for PRA, serum aldosterone, K. DNA collection for genetic testing is optional.
- 8) Cardiac MRI for ECV, endo to epicardial flow (perfusion) ratio, diastolic and systolic strains and peak strain rates, LVEF and LV mass.
- 9) Abdominal MRI for VAT and SAT.

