- 5) Standardized lifestyle counseling as per goals derived from the AACE and NCEP-ATP III guidelines and modeled after the Diabetes Prevention Program. At the 1 week visit, the study dose will be escalated to 50mg twice daily as tolerated based on blood pressure and labs.

12 Month Visit: Same as Baseline Visit 1

Substudy Visit 2 (Optional): Same as Substudy Visit 1

COVID19 Contingency Plan: MGH and BWH have instituted restricted visits for research purposes in response to the evolving COVID-19. These restrictions have prompted the following changes to the study:

1) We may conduct visits remotely until restrictions are lifted. Remote visits will be conducted over zoom video conferencing or telephone and every attempt will be made to keep the visit schedule the same. Changes may occur to the visit schedule due to factors related to covid19. During these visits, someone from the study staff will contact the subject (via zoom video conferencing or telephone) and may conduct the following research activities:

- Consenting*
- Obtaining information about past and present health
- Questionnaires
- Lifestyle Counseling
- Obtaining information related to safety assessments

2) We may ship study drug directly to the subject.

3) If blood work cannot be obtained at the study site, we may ask the subject to have labs performed locally. We will provide a lab requisition and help locate a facility.

4) We will try to arrange for assessments to occur remotely and continue to follow the visit schedule. Some study procedures require a visit to the study site, for example, imaging procedures. We may provide the subject with additional study drug until we are able to perform the study procedure, and this may extend the visit schedule. If a study procedure requires an in-person visit and cannot be scheduled at the study site due to

Mineralocorticoid Receptor Antagonism for Cardiovascular Health in HIV The MIRACLE HIV Study

COVID19 policies, then the procedure may be omitted.

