Statistical Consideration: Aim I: The primary endpoint is change in CFR assessed by cardiac PET or change in sMBF by cardiac MRI. Secondary endpoints will include the following: change in sICAM and sVCAM. Shapiro-Wilk test will be used to assess for normality of distribution, and variables that are not normally distributed will be appropriately transformed prior to inclusion in multivariable models. We will compare the change in CFR from months 0 to 12 between treatment groups (eplerenone vs. placebo) using student's t-test for variables that are normally distributed or Wilcoxon rank sum test for variables that are not normally distributed. We will also compare changes in sICAM and sVCAM over 12 months between treatment groups using similar statistical methods. In all Aims, for subjects who withdraw after 6 months, but before the final 12 month visit, we will obtain biomarkers and imaging similar to that scheduled for the final 12 month visit if the subject agrees to have end of study testing. The analysis will be intention to treat (ITT). In order to properly handle subjects with missing outcomes (those who withdrew before 12 months), we will apply longitudinal linear mixed effects model analysis with random subject level intercepts and time slopes by which the longitudinal treatment effect can be examined by testing the significance of

Mineralocorticoid Receptor Antagonism for Cardiovascular Health in HIV The MIRACLE HIV Study

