time x treatment interaction, which will provide unbiased effect estimate under missing at random condition, which will be carried out by using augmented data sets created by multiple imputation. A sensitivity analysis will be performed to include only those subjects who completed the study. Baseline variables will be compared between treatment groups, and any variable that is statistically different between groups will be controlled for using multivariable modeling. It may be that subjects with more significant RAAS activation and dysregulation in aldosterone at baseline) are more responsive to eplerenone. We will phenotype the RAAS in subjects at the low sodium visit and, guided by this data, may use aldosterone levels prior to intervention as an index of RAAS activation and a covariate in assessing treatment response, to determine if eplerenone is more effective in the subpopulation with greater baseline aldosterone dysregulation and RAAS activation. Covariates that will be considered for inclusion in modeling, include variables that differ at baseline and those variables that may affect vascular dysfunction, inflammation, fibrosis and plaque (age, race, gender, BP, tobacco/illicit drug use, family history of CVD, lipids, and glucose), HIV parameters (viral load, CD4, and duration of HIV and ART use) and compliance. This will permit us to assess relevant factors that may mediate the effect of eplerenone on CFR in HIV and interactions between HIV and traditional risk factors contributing to eplerenone effects. Moreover, we will compare changes in CFR and vascular biomarkers over 12 months using regression analysis. We will perform Pearson's correlation for variables that are normally distributed and Spearman's correlation for variables that are non-normally distributed. If we see significant changes in specific biomarkers that correlate with changes in CFR, then we will run those specific biomarkers from stored serum at earlier time points (e.g. 6 months) to see if early changes in biomarkers can predict changes in CFR, as well as predict response to MR blockade. **Biostatistician Role:** The biostatistician will monitor data collection, quality and completeness of the study throughout all years of the grant. The biostatistician will create the randomization plan, using a permuted block algorithm, stratified for gender, statin use, and presence of plaque and provide the list to the study pharmacist (investigators will remain blinded). Identical placebo will be provided by the pharmacy. **Sample Size Determination:** Preliminary data from HIV subjects presented in this grant demonstrate a CFR 1.74 ± 0.73 (mean \pm SD) using cardiac PET. Supportive data are also derived from a longitudinal study by our team using cardiac PET, showing mean \pm SD change of CFR in diabetics treated with spironolactone 0.33 ± 0.83 vs. placebo: 0.02 ± 1.03 over 6 months (mean SD=0.93).⁴⁰ Given these data, we considered the range 0.73 - 0.93 SD to accurately reflect the potential variability of change in CFR for the proposed study. Based on this data, we now provide a range of detectable differences using 85% power and a revised increased sample size of 80 subjects, with an attrition rate of 15%, leaving 68 evaluable subjects. Thus, even choosing a conservative SD of 0.93, the study will be well powered to detect a difference in mean change of CFR of at least 0.69. As our preliminary data, using PET, show that HIV patients have a mean CFR 1.7, an increase of CFR to 2.4 with eplerenone is a clinically relevant increase associated with decreased morbidity and mortality. For the sMBF and biomarkers, this study has 85% power at a two-sided 0.05 α level to show a change in the variable of at least 0.74 SD after treatment with eplerenone vs. placebo.

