Cardiac PET and Radiation: The two cardiac PET scans will involve exposure to radiation for research purposes. Subjects will receive a research related rest and stress ^{13}N -ammonia PET scan before and after a mineralocorticoid receptor antagonist. ^{13}N -ammonia (20 mCi) will be injected twice prior to rest and stress scans. Each PET scan will expose subjects to 3.36 mSv of radiation. The added radiation from the two PET scans (baseline and follow-up) will be 6.72 mSv. This is equivalent to the amount of radiation an individual would normally get in 2 years and 2 months from natural background sources from the earth and the sky. The radioactive tracer will be administered at baseline and at 12 months. HIV patients may have silent ischemia. We will assess the first regadenoson/adenosine-stimulated coronary blood flow study for this condition. Any subject with evidence of clinical significant ischemia will be withdrawn from the study prior to further evaluative studies and prior to randomization to study drugs. Subjects with evidence of ischemia will be referred to a cardiologist for appropriate evaluation and treatment. In addition, there may be incidental findings on the PET study. If any of these findings are clinically significant, the subjects will be withdrawn from the study and referred to the primary care physician for further evaluation.

Regadenoson/Adenosine: Regadenoson or adenosine will be administered during the cardiac PET and MRI studies. Regadenoson stress and adenosine stress have been used routinely for many years for evaluating patients with known or suspected CAD. Regadenoson and/or adenosine will be administered at the radiologist's discretion. The most common side effects associated with the Regadenoson or adenosine infusion include: flushing, chest pain/pressure, shortness of breath, palpitations, headache, mild hypotension and heart block. These side effects are usually mild and self-limiting. If they are severe in intensity, aminophylline IV (1 mg/kg) will be given as per standard protocol. Subjects will have their blood pressure and heart rate monitored closely by a physician and/or nurse in attendance at all times. The protocol will be immediately discontinued if clinically significant atrial or ventricular arrhythmias are observed.

MIneralocorticoid Receptor Antagonism for CardiovascuLar hEalth in HIV The MIRACLE HIV Study

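### For endpoints imaged only twice, the random-slope model has more variance parameters than the data can separate, and the stated test on change leaves baseline precision unused

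*Combined protocol and SAP*

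**What the plan says.** Section VI (Aim I) gives the comparison of arms: "We will compare the change in CFR from months 0 to 12 between treatment groups (eplerenone vs. placebo) using student's t-test", with a rank-sum test if the data are not normal. For subjects whose final outcome is missing, the intention-to-treat analysis uses a "longitudinal linear mixed effects model analysis with random subject level intercepts and time slopes". It tests the "time x treatment interaction, which will provide unbiased effect estimate under missing at random condition", and is "carried out by using augmented data sets created by multiple imputation". Aims II, III and V take over these methods.

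Each imaging endpoint is scheduled twice:

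- **CFR (PET):** Section VII states "The radioactive tracer will be administered at baseline and at 12 months".
- **PET and cardiac MRI (CFR, sMBF, ECV):** Section V has "12 Month Visit: Same as Baseline Visit 1", with no imaging visit in between.
- **Plaque (CTA):** once at Screening Visit 2, then "Coronary CTA only at the end of study visit prior to 12 Months".
- **TBR (FDG-PET/CT):** "Substudy Visit 2 (Optional): Same as Substudy Visit 1".

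The 6-month safety visit adds blood markers only. Two provisions allow scans off schedule. Subjects who withdraw after 6 months may have their final imaging early (Section VI), and the COVID-19 contingency plan may delay it (Section V).

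On covariates, Section VI adjusts for variables that turn out to differ significantly between arms and lists others that may be considered. The baseline value of the outcome is not listed. Of the three stratification factors, gender is listed; statin use and presence of plaque are not. The plan does not state whether time is nominal or actual, whether the mixed model has a treatment main effect or a shared baseline mean, or what to do if the covariance structure cannot be estimated.

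**The concern.** There are two separate matters. First, a random intercept, a random slope, their covariance and a residual variance cannot all be learned from two measurements per subject at fixed times. Software may then fail to converge, or may converge without warning on an arbitrary split of the variance, and the plan gives no fallback. Second, a test on raw change ignores how far the baseline value predicts the 12-month value. Adjustment triggered by a significant baseline difference makes the model depend on the data and does not reliably recover that information. At stake is power for the primary endpoint and the main imaging endpoints of three further aims, together with modelling choices left open until data exist.

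**Working it through.** **1. Parameter count.** Code baseline as 0 and 12 months as 1. Let a be the intercept variance, c the intercept-slope covariance, b the slope variance and s the residual variance. Then:

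- Var(baseline) = a + s
- Cov = a + c
- Var(12 months) = a + 2c + b + s

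That is four unknowns and three equations. Replacing (s, a, c, b) by (s + d, a − d, c + d, b − 2d) leaves all three unchanged. In simulated data, residual variances of 0.02, 0.10 and 0.20 gave the same fit with slope variances 1.19, 1.03 and 0.83, which matches b − 2d (1.19 − 2 × 0.08 = 1.03; 1.03 − 2 × 0.10 = 0.83). The rank of the mapping is 3. Adding subjects with a baseline scan only does not raise it.

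**2. Effect on the treatment estimate.** In another simulated trial, residual variances of 0.01, 0.1, 0.2 and 0.3 gave the same log-likelihood, the same time-by-treatment estimate (0.7545) and the same standard error (0.2098). These equal the t-test on change. The equality holds for complete data with a treatment main effect in the model.

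**3. Off-schedule scans.** With actual time and some scans between 6 and 12 months, the rank becomes 4. The assumed variances were 0.30 (intercept), 0.50 (slope) and 0.23 (residual), with covariance −0.1. Adding 6 early-scanned subjects to 68 gives a standard error of 0.75 for the slope variance (true 0.50) and 0.36 for the residual variance (true 0.23). The model is then identified, but only weakly. With three times (0, 6 and 12 months) the rank is also 4, so biomarkers with a 6-month value are not affected.

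**4. The plan's own CFR figure.** Inputs from Section VI: 80 enrolled, 15% attrition, so 80 × 0.85 = 68 evaluable, 34 per arm; SD of change 0.93; two-sided 0.05; 85% power. The noncentral t gives a detectable difference of 0.7375 SD, and 0.7375 × 0.93 = 0.686. The stated 0.69 and 0.74 SD are reproduced.

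**5. Gain from baseline adjustment.** With SDs s0 and s1 at the two visits and correlation r:

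- Var(change) = s0² + s1² − 2·r·s0·s1
- Var(baseline-adjusted) = s1²(1 − r²)
- The difference is (s0 − r·s1)², which is never negative.

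With s0 = s1 the ratio of adjusted to change variance is (1 + r)/2. Simulation gave 0.754 against 0.75 at r = 0.5, and 0.846 against 0.85 at r = 0.7. The detectable CFR difference is 0.686 × √((1 + r)/2):

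| r | Variance ratio | Detectable difference | Power at 0.69 |
|---|---|---|---|
| Change score | 1 | 0.69 | 85% |
| 0.5 | 0.75 | 0.59 | 94% |
| 0.7 | 0.85 | 0.63 | 90% |
| 0.8 | 0.90 | 0.65 | 89% |

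The few degrees of freedom spent on covariates, out of 66, are ignored.

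**6. ECV.** Section VI (Aim II) states r = 0.7, SD of change 0.03 and a difference of 0.02. The variance ratio is (1 + 0.7)/2 = 0.85, a fall of 15%. The adjusted SD is 0.03 × √0.85 = 0.0277. With 34 per arm, power at exactly 0.02 rises from 77% to 84%, and the detectable difference falls from 0.0221 to 0.0204. The starting power is 77% rather than the stated 85% because 0.0221 has been rounded to 0.02.

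**The case against.** The strongest reply is that nothing the plan tests is harmed. Only the split of nuisance variance is unidentified, while the time-by-treatment effect and its standard error are the same for every split. That stands. A reader might infer that the intention-to-treat analysis cannot be carried out, or that it is biased; step 2 shows otherwise.

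A reader might also infer that the mixed model itself wastes the baseline data by fitting separate baseline means. The documents do not say so. They name only the interaction, and a model with time and time-by-treatment terms but no treatment main effect already has a shared baseline mean. The fair statement is that this is unspecified. Nor is the model merely a t-test in another form when outcomes are missing, because it also uses the baseline values of subjects who drop out.

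A t-test on change is valid in a randomised trial, so baseline adjustment improves efficiency and does not repair an error. That also stands. The size of the CFR gain does depend on an unstated correlation. A larger gain, to 0.53, can be computed from r = 1 − 0.93²/(2 × 0.73²) = 0.19. That value combines a cross-sectional SD in HIV with a change SD from a trial in diabetics, and should not be relied on.

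Finally, fitting a mixed model to multiply imputed data is not wrong, and imputation can use further information such as the 6-month markers. There is no ground for asking that one of the two be removed.

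What the reply does not answer is that the stated comparison is unadjusted, that the baseline value enters only through a significance rule, and that time scale, baseline parameterisation and fallback are left open.

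**Conclusion.** The point holds as one of specification and efficiency. For endpoints with two scheduled scans, the random-intercept and random-slope model is over-parameterised at fixed visit times, and off-schedule scans identify it only weakly if actual time is used. No bias, inflated type I error or loss of validity follows from this. The stated 0.69 is correct for a change-score analysis.

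The practical loss is precision. For CFR, the detectable difference could be about 0.59 to 0.65 instead of 0.69, and power at 0.69 could be 94% to 89% instead of 85%. This assumes equal variances at both visits and a correlation of 0.5 to 0.8. For ECV the correlation is the plan's own, and the 15% fall in variance needs only the equal-variance assumption. Biomarkers measured at three or more times are outside the point.

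**What to change.** For CFR, sMBF, ECV, noncalcified plaque volume and TBR, name one main analysis in advance. It can be either ANCOVA of the 12-month value on the baseline value, or a two-visit model with unstructured covariance and a common baseline mean across arms. Include the three stratification factors (gender, statin use, presence of plaque). For this analysis, drop the rule of adjusting for variables that differ significantly at baseline. State whether time is nominal or actual, and so how early and delayed scans enter.

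Keep random slopes only for biomarkers with three or more time points. Multiple imputation may stay. The change is to the wording of Section VI and needs no further data, visits or subjects.

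### Baseline aldosterone as a covariate cannot show in whom eplerenone works better; if this optional analysis is run, it needs an interaction with treatment

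*Combined protocol and SAP*

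**What the plan says.** All of this is in section VI, Biostatistical Analysis, under Aim I.

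- **Hypothesis.** "It may be that subjects with more significant RAAS activation and dysregulation in aldosterone at baseline) are more responsive to eplerenone". This is a statement about effect modification.
- **Method.** After the low-sodium visit the investigators "may use aldosterone levels prior to intervention as an index of RAAS activation" and as "a covariate in assessing treatment response, to determine if eplerenone is more effective in the subpopulation with greater baseline aldosterone dysregulation". The wording is permissive, and the choice is to be guided by the low-sodium data.
- **Primary comparison.** "We will compare the change in CFR from months 0 to 12 between treatment groups (eplerenone vs. placebo) using student's t-test", or a rank-sum test if the data are not normal.
- **Longitudinal model.** A linear mixed model, in which the treatment effect is the "time x treatment interaction, which will provide unbiased effect estimate under missing at random condition". This is the only model interaction that the plan specifies.
- **Other mention of interactions.** "interactions between HIV and traditional risk factors contributing to eplerenone effects". Aldosterone is not named there.

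Aims II, III and V reuse the Aim I methods, so the same wording governs ECV, plaque and TBR.

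**The concern.** The question and the method do not match. To ask whether the drug works better at higher aldosterone is to ask whether the treatment effect changes with aldosterone. A model with treatment and aldosterone as separate terms forces that effect to be the same at every aldosterone level.

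Two errors could follow. A significant aldosterone coefficient could be reported as evidence of differential response when aldosterone only predicts change in CFR in both arms. Or a null coefficient could be read as no differential response when the arms' slopes differ and cancel on averaging. Because the use of aldosterone is left open until the low-sodium data have been seen, the form of the model should be fixed beforehand.

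**Working it through.** **1. Reproduce the plan's own figure.** Inputs from the Aim I sample-size paragraph: "using 85% power and a revised increased sample size of 80 subjects, with an attrition rate of 15%, leaving 68 evaluable subjects"; SD of change in CFR 0.73 to 0.93; detectable difference 0.69 at SD 0.93. Allocation is 1:1. A two-sided alpha of 0.05 is stated for sMBF and biomarkers and is assumed here for CFR.

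- 80 x 0.85 = 68, or 34 per arm.
- Normal approximation: (1.96 + 1.036) x sqrt(2/34) = 0.727 SD; x 0.93 = 0.68.
- Noncentral t, 66 df: 0.686 at SD 0.93 and 0.538 at SD 0.73. Power at 0.69 with SD 0.93 is 85.4%.

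The stated 0.69 reproduces. It sizes the overall treatment effect; no figure is given for the aldosterone question.

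**2. What the covariate coefficient measures.** Let the slope of change in CFR per SD of aldosterone be p on placebo and e on eplerenone. With 1:1 allocation the main-effect coefficient is about (p + e)/2. Effect modification is e - p.

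- p = 0.4, e = 0.4 (prognosis only): average 0.4, difference 0.
- p = 0, e = 0.8 (strong modification): average 0.4, difference 0.8.
- p = -0.4, e = 0.4 (modification with opposite slopes): average 0, difference 0.8.

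The first two cases give the same coefficient and opposite answers.

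**3. Simulation check.** 68 subjects, residual SD 0.93, average treatment effect 0.69, 8,000 runs per case. The slopes are assumptions chosen to illustrate the point.

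| Slopes (placebo, eplerenone) | Covariate significant | Interaction significant |
|---|---|---|
| 0.4, 0.4 | about 92% | about 5% |
| 0, 0.8 | about 86% | about 91% |
| -0.4, 0.4 | about 7% | about 91% |

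In every case the main-effect model returns a single treatment effect of about 0.69.

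**4. Precision of the correct term.** For a standardised continuous covariate with 1:1 allocation, the SE of e - p is about 2 x SD/sqrt(68). The detectable value at 85% power is (1.96 + 1.036) x 2/sqrt(68) = 0.727 SD.

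- SD 0.73: 0.727 x 0.73 = 0.53 (0.54 by t, 64 df).
- SD 0.93: 0.727 x 0.93 = 0.68 (0.69 by t, 64 df).

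So the effect would have to shift, per SD of aldosterone, by about as much as the whole difference the trial is sized to detect.

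A median split (assumed 17 per cell) has SE = SD x sqrt(4/17). The detectable difference between subgroup effects is then 1.08 to 1.37 CFR units, and power for a difference of 0.69 is 48% at SD 0.73 and 33% at SD 0.93.

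**5. Which term in which model.** In a change-score regression the term is treatment x aldosterone. In the mixed model the treatment effect is already a time interaction, so the term is time x treatment x aldosterone. With two time points, no modification at baseline and 0.8 per SD at month 12, a two-way treatment x aldosterone term without time averages the two visits: (0 + 0.8)/2 = 0.4. That is half the true value.

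**The case against.** The plan never says that aldosterone enters as a main effect only. It gives an effect-modification purpose, and a statistician could reasonably implement the sentence with an interaction. The later phrase, "interactions between HIV and traditional risk factors contributing to eplerenone effects", shows that modification of the drug's effect was in mind. The analysis is also optional. All of that is fair, and it limits the weight of the point. It does not supply the missing term: an interaction has to be inferred, and the one model interaction written down is time x treatment.

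Some stronger readings are tempting, and the documents do not support them:

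- **That the covariate coefficient says nothing about modification.** It does move when one arm's slope changes (second row of the table). What it cannot do is separate modification from prognosis. The opposite-slopes row is a special case.
- **That this is the trial's central hypothesis, or the sole reason for the low-sodium visit.** The Specific Aims list no hypothesis that baseline aldosterone modifies the effect of eplerenone. The visit is described as RAAS characterization, and Aim IV also uses the sodium-restricted state.
- **That the plan commits to this analysis.** The wording is permissive.

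**Conclusion.** The point holds as a mismatch between a stated question and a stated method in an optional secondary analysis. Followed literally, the model gives one common treatment effect, and its aldosterone coefficient cannot separate prognosis from differential response.

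Even correctly specified, the analysis is exploratory: 85% power needs a change in treatment effect of about 0.53 to 0.68 CFR units per SD of aldosterone, or 0.54 to 0.69 by t. This assumes 34 evaluable subjects per arm, a two-sided alpha of 0.05, a common residual SD equal to the plan's 0.73 to 0.93, and an approximately linear relation with aldosterone.

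A reader might infer that the main result or the sample size is compromised. Neither is: the primary comparison does not use aldosterone, and the 0.69 reproduces.

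**What to change.** In section VI, Aim I, state before unblinding that, if the analysis is done:

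1. The term of interest is treatment x baseline aldosterone in a regression of the change score, or time x treatment x aldosterone with all lower-order terms in the mixed model.
2. Aldosterone is one named pre-treatment measure from Baseline Visit 2, either the serum level or 24-hour urinary excretion. It is kept continuous, and transformed if skewed, as the plan already provides for non-normal variables.
3. The interaction estimate is reported with its 95% CI and labelled exploratory, with the low power stated. Treatment effects at two or three aldosterone values would help the reader but are a matter of presentation.
4. The aldosterone main effect is not interpreted as evidence of differential response.
5. The same wording applies wherever Aims II, III and V reuse the method.

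The cost is one extra term, plus lower-order products in the mixed model, and a low-powered estimate. Both measures are already collected before study drug starts, so no new data or subjects are needed.
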